Participants in this study are patients with hypotension, who have undergone evaluation as part of our “The Pathophysiology of Orthostatic Hypotension” protocol (IRB#030752, CRC approval pending). Based on the results of these studies, we will administer medication which we believe might improve their symptoms. We will first test a single dose of one or more drugs with monitoring for 24 hours. A drug or drugs effective at preventing an orthostatic fall in blood pressure might then be tested in a 5-day crossover trial with comparison of effects to placebo. Based on the results of the 5-day trial, a patient might then be given a 2-month trial of the drug, with periodic admissions to the GCRC for assessment of symptoms. The period of time needed to complete this study will depend on the number of medications tested.

Drug withdrawal

Participants must remain off any medications that could affect blood pressure for three days prior to and during study. This includes not only their usual scheduled medications, but also other drugs that might be taken intermittently. If their symptoms are severe enough that they or their physician have concerns that their symptoms may worsen, they may be admitted to the hospital for observation during this portion of the study. While they are an inpatient on the GCRC, their general condition, blood pressure and heart rate will be checked regularly to reduce any risk.

Urine pregnancy test

We will perform a urine pregnancy test every time female participants are admitted to the hospital for this study.

Diet

We will ask study participants to eat a standard diet with no caffeine, 150-mEq/day sodium, 70 mEq potassium, and no substances that interfere with catecholamine synthesis, release or assay for three days prior to and during testing.

24-Hour Urine Collection

Participants will collect their urine for 24 hours every time they are admitted to the hospital for this study. The urine will be analyzed for sodium, potassium, creatinine, and catecholamines.

Orthostatic vital signs

Orthostatic vital signs will be measured several times a day. This testing consists of blood pressure and heart rate measured while patients are lying down and then repeated after standing quietly for 5 minutes, using the Dinamap.

Single-dose drug trials

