Participants will be admitted to the Vanderbilt Clinical Research Center the evening prior to the study. In the morning, the patients will be seated or in bed for a 30 min baseline period of blood pressure and heart rate monitoring. The medication will be given by mouth, and blood pressure and heart rate will be monitored every 10-15 minutes for the first hour, using a Dinamap. Orthostatic vital signs will be taken after 1, 2, 3, 4, 8, and 12 hours. Fifteen ml of blood will be collected through a saline lock during baseline and after 2, 4, and 8 hours while in the supine and standing positions to measure catecholamines (total of 4 samples lying down and 4 samples upright). Aldosterone will also be measured in blood collected during baseline and at one other timepoint, depending on the duration of the drug effect (total of 2 samples lying down and 2 samples upright). A second blood sample will be collected with the aldosterone and an aliquot of plasma frozen for possible analysis of plasma renin activity. Urine will be collected from 0-7 hours, 7-12 hours and 12-24 hours for measurement of catecholamines. Depending on how well the drug is tolerated and the degree of improvement in orthostatic vital signs and symptoms following the drug, another single-dose drug trial might be scheduled 48 hours after the first or the patient might be asked to start a 5-day trial of the drug at that time. If they are not scheduled for another trial at this time, they can be discharged. The medications include domperidone, metyrosine, L-DOPS, alpha-methyldopa, L-dopa, carbidopa, atomoxetine, and placebo.

Single-dose trial

Time	Days 3,2 pre-study	Day 1 pre-study	Study Day							
			0 hr	1 hr	2 hr	3 hr	4 hr	8 hr	12 hr	24 hr
Drug/diet restriction	X	X	X	X	X	X	X	X	X	X
Urine collection		X	X	X	X	X	X	X	X	X
Admission to GCRC		X								
Pregnancy test		X								
Drug administration			X							
Blood sample			X				X	X	X	
Vital signs		X	X	X	X	X	X	X	X	

5-Day drug trials

Once the appropriate dose has been decided, we will conduct a single-blinded crossover trial. Depending on where they live and the severity of their symptoms, participants might be able to go home

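### Do the single-dose tests lack a pre-dose lying and standing blood pressure and a defined start for the 48-hour gap?

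*Combined protocol and SAP*

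**What the plan says.** The section on single-dose drug trials describes the pre-dose period as follows: "In the morning, the patients will be seated or in bed for a 30 min baseline period of blood pressure and heart rate monitoring". After the dose, "Orthostatic vital signs will be taken after 1, 2, 3, 4, 8, and 12 hours". Blood is collected "during baseline and after 2, 4, and 8 hours while in the supine and standing positions to measure catecholamines". The next step is chosen "Depending on how well the drug is tolerated and the degree of improvement in orthostatic vital signs and symptoms following the drug". One option is that "another single-dose drug trial might be scheduled 48 hours after the first". The alternative is to begin the 5-day trial at that point.

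The single-dose table has a vital signs row marked on Day 1 pre-study, at 0 hr, and at 1, 2, 3, 4, 8 and 12 hr. It does not give the posture.

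Four other places bear on the point:
- The section on orthostatic vital signs defines them as "blood pressure and heart rate measured while patients are lying down and then repeated after standing quietly for 5 minutes" and has them taken repeatedly each day.
- The section on drug withdrawal says "Participants must remain off any medications that could affect blood pressure for three days prior to and during study", and goes on to name the patient's scheduled and occasional drugs.
- Experimental Design and Methods gives each single-dose test 24 hours of monitoring. It lets a drug that prevents the fall in pressure on standing go forward to a placebo-controlled 5-day crossover.
- The justification for GCRC use anticipates no data analysis, while Biostatistics lists paired within-subject methods that might be needed.

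**The concern.** Improvement is a comparison. To say that the drop on standing became smaller after a drug, one needs the drop before it. The text puts the patient seated or in bed before the dose and starts the listed orthostatic readings at 1 hour. Taken alone, it leaves the pre-dose reference undefined, and a good or bad day could be mistaken for a drug effect.

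The interval raises a second doubt. If 48 hours is counted from dosing, an earlier study drug was taken inside the three days that the drug withdrawal section and the table keep free of drugs, provided a study drug counts as one. A residual effect on pressure or catecholamines could then colour the next test. These tests guide which drug each patient takes into the 5-day trial, so the choice for that patient is what would be at stake.

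**Working it through.** The plan gives no figure to reproduce here. The check is a comparison of the text with the table, plus arithmetic on the interval.

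**1. Is a pre-dose orthostatic reading planned?**

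| Source | Before dose | After dose |
|---|---|---|
| Text, pressure and heart rate | 30 min, seated or in bed | orthostatic at 1, 2, 3, 4, 8, 12 h |
| Table, vital signs row | Day 1 pre-study and 0 hr | 1, 2, 3, 4, 8, 12 hr |
| Text, blood for catecholamines | lying and standing | lying and standing at 2, 4, 8 h |

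The post-dose marks in the table are exactly the orthostatic times in the text. The natural reading is that the row means orthostatic vital signs throughout, including the two pre-dose marks. The patient already lies and stands for baseline blood, so the matching pressures need no further change of posture.

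**2. How long is the gap?**
- Counted from the dose: 48 h from dose to dose, which is 72 − 48 = 24 h less than three days.
- Counted from the end of monitoring: 24 + 48 = 72 h from dose to dose, which equals three days.

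**3. How much carry-over could there be?** The documents give no half-lives, so 6, 12 and 24 h are assumed for the effect. Share remaining = 2^(−t / half-life), as a percentage of the earlier drug's own effect.

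| Time since earlier dose | 6 h | 12 h | 24 h |
|---|---|---|---|
| 48 h | 0.39% | 6.25% | 25% |
| 72 h | 0.02% | 1.56% | 12.5% |
| 168 h | <0.001% | 0.006% | 0.78% |

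The last row is the 5-day branch: 48 h plus 5 days (120 h) from study day 0 to the first Posture Study.

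**4. Would analysing change from 0 hr help?** With a 48 h gap, the carry-over in the raw reading is the share left at that time. In the change it is the share at 48 h minus the share at the reading, with opposite sign.

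| Reading after next dose | Measure | 6 h | 12 h | 24 h |
|---|---|---|---|---|
| 4 h (52 h) | raw | 0.25% | 4.96% | 22.3% |
| 4 h | change | 0.14 points | 1.29 points | 2.73 points |
| 12 h (60 h) | raw | 0.10% | 3.13% | 17.7% |
| 12 h | change | 0.29 points | 3.13 points | 7.32 points |

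Change helps for slow effects and early readings. At 12 h it makes no difference for a 12 h half-life and is worse for a 6 h half-life, although both amounts are tiny at 6 h.

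The change also carries noise. Its variance relative to the post-dose value is 2(1 − r), where r is the same-day correlation within a patient: 1.4 at r = 0.3, 1.0 at 0.5 and 0.6 at 0.7 (values of r assumed).

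**The case for a change.** The best case for a change is that no sentence requires a lying and standing pressure before the dose or names the comparator. The 0 hr mark could equally stand for the seated or in-bed baseline, and Day 1 pre-study is a different day. The table as extracted also disagrees with the text on blood sampling (0, 4, 8 and 12 hr against baseline, 2, 4 and 8 h), so it is a weak basis for filling gaps, though that may be an extraction fault. Placebo is among the single-dose medications, but nothing says every patient receives it, so it is not an assured reference. Stating the posture would cost almost nothing.

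What stands is that the posture at 0 hr and the start of the 48 hours are unstated. The step from an unstated posture to an absent reading does not stand. Nor does the claim that everything turns on the pre-dose reading. Tolerability and symptoms also count, and whether a drug prevents the fall on standing can be seen in each post-dose lying and standing pair. A drug wrongly favoured would still face placebo if tested in the crossover. For a drug wrongly passed over, no section rules out a second test.

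On the interval, the drug withdrawal section can fairly be read as covering the patient's own medicines only, and counting from the end of monitoring gives 72 h. It is therefore an ambiguity and not a proven contradiction.

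**Conclusion.** No change to the plan follows. The pre-dose point is missing detail that staff would very likely fill sensibly, because the table row, the general rule on orthostatic readings and the baseline blood draws all point to a lying and standing reading before the dose. An analyst would take that reading as the day's reference.

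The interval is 48 or 72 h depending on where the count starts. Its effect ranges from negligible to a quarter of the earlier drug's effect at 48 h, wholly according to the assumed half-life, and is at most 0.8% for the first Posture Study of the 5-day branch. Requiring change scores would be a preference with mixed returns, in a study that expects a per-patient judgement rather than a formal analysis at this step.

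If the protocol is reopened for another reason, the drug withdrawal section, the single-dose section and its table should be reconciled on when the interval starts and whether an earlier study drug counts. Which interval is right is a clinical matter on which this review takes no view.

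The conclusion assumes that the table row means orthostatic readings throughout and that carry-over decays exponentially.

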Occasionally, patients present to the Autonomic Dysfunction Center with a unique constellation of

symptoms of autonomic dysfunction so that they do not fit into a diagnostic category (Orthostatic Intolerance, Pure Autonomic Failure, Multiple System Atrophy, Baroreflex Failure). Some of these patients have severe orthostatic hypotension and resemble those with DBH deficiency, but they do not have the extreme plasma levels of DA. We propose that medication trials in these patients will assist us in optimizing their treatment. Evaluation will be undertaken under controlled conditions with medication and dietary restrictions and will consist primarily of orthostatic blood pressure and heart rate measurements and plasma catecholamine determinations.

Participants will first take part in a study designed to provide information on the pathophysiology of their autonomic problems (The Pathophysiology of Orthostatic Hypotension, IRB#030752, CRC approval pending). Results from this study will help us determine which drug(s) to administer in the proposed protocol.

PRELIMINARY STUDIES

Once the pathophysiology of DBH deficiency was understood, we were able to rapidly develop a specific and effective therapy. Consistent with DOPA and DA reducing blood pressure, the administration of a tyrosine hydroxylase inhibitor, such as metyrosine, raises blood pressure in DBH-deficient individuals. The pressor effect appears to correlate with the metyrosine-associated reduction in plasma DA and DOPA levels and also urinary DA levels. DOPS, or Droxidopa INN:(-)-threo-3-(3, 4-dihydroxyphenyl)-L-serine, is structurally closely related to NE, but has an additional COOH group. It can be pumped up into the noradrenergic nerves and converted into NE by L-aromatic amino-acid decarboxylase without requiring DBH. L-DOPS has been used effectively in the treatment of patients with complete DBH deficiency. It might also improve the blood pressure in patients that have profound orthostatic hypotension but do not appear to have complete DBH deficiency.

EXPERIMENTAL DESIGN AND METHODS

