for part of this study. However, after 4 days on the drug (or placebo), they will be admitted to the GCRC. They will be supine and NPO after midnight. In the morning, we will do a Posture Study to determine the effectiveness of the treatment. Before breakfast, we will draw 15 ml of blood while they are supine and another 15 ml after they have stood for 30 minutes to measure catecholamines and aldosterone. A second blood sample will be collected with the aldosterone and an aliquot of plasma frozen for possible analysis of plasma renin activity. We will monitor blood pressure and heart rate during this study, using a Dinamap. Standing time will be determined, and the participants will be asked about their symptoms periodically during the study. For at least three days following this testing, participants will take no medication. They will then start a 5-day regimen of the medication, if they previously took the placebo, or placebo, if they previously took the medication. They will not be told whether they are taking active drug or placebo. The Posture Study will be repeated in the GCRC after the second 5-day period.

5-day trial

Time	Day 3 pre-study	Days 1,2 pre-study	Study day 0	Study days 1,2,3		Study day 4	Study day 5	Study days 6,7		Study day 8	Study days 9,10,11			Study day 12	Study day 13
Drug/diet restriction	X	X	X	X	X	X	X	X	X	X	X	X	X	X	X
Urine collection						X								X	
Admission to GCRC						X								X	
Pregnancy test	X														
Drug/placebo administration			X	X	X	X				X	X	X	X	X	
Posture study/Blood sample							X								X
Vital signs						X	X							X	X

Depending on the results of the 5-day trial, participants will be given a longterm trial of a drug. At the initiation of treatment, and after two weeks, four weeks, and eight weeks of drug, they will be evaluated by a posture study, 24-hour urine collection and assessment of their symptoms. The dose of the medication will be adjusted after two and four weeks of treatment if there has been insufficient improvement in blood pressure (able to stand with < 20 mmHg decrease in systolic blood pressure) or symptoms.

Chronic trial

Days	-3,-2	-1	0	1-10	11,12	13	14	15-24	25,26	27	28	29-52	53,54	55	56
Restrict diet	X	X	X		X	X			X	X	X		X	X	X
Collect urine		X				X				X				X	
Admit to GCRC		X				X				X				X	
Pregnancy test		X				X				X				X	
Take Drug			X	X	X	X	X	X	X	X	X	X	X	X	
Posture study/ Collect blood			X				X				X				X
Vital signs		X	X			X	X			X	X		X	X	X
Adjust dosage							X				X				

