BIOSTATISTICS

Statistical analyses will be performed on a personal computer with the statistical package SPSS for Windows (Version 10.0, SPSS, Chicago). Some paired comparisons (Paired t-test, Wilcoxon signed-rank test, repeated measures ANOVA, Friedman ANOVA by ranks) might be needed to compare treatment responses within a subject.

Protection of Human Subjects:

POPULATION:

The conduct of these studies will involve approximately 25 human subjects. Subjects will include patients with severe orthostatic hypotension and other autonomic symptoms who do not meet criteria for one of our standard diagnoses. Potential study participants will first take part in "The Pathophysiology of Orthostatic Hypotension" (IRB #030752, CRC approval pending). Results from that study will provide information on the pathophysiology of the autonomic disorder and might suggest which medication(s) might be an effective treatment. Subjects will range in age from 18-70 and be non-smokers, drug-free, able to give informed consent, and free of pulmonary, renal, hematopoietic, hepatic and cardiac disease. Exclusion criteria for the study include smoking, pregnancy, medications affecting the autonomic nervous system, any chronic illness, and anemia (Hct<35).

RESEARCH MATERIALS:

Research materials include blood, urine, and data. The blood will be analyzed for catecholamines, renin and aldosterone. Urine will be analyzed for catecholamines, sodium, potassium, and creatinine.

RECRUITMENT OF SUBJECTS:

We will recruit patients from those referred to the physicians of the Autonomic Dysfunction Center at Vanderbilt who have participated in "The Pathophysiology of Orthostatic Hypotension" (IRB #030752, CRC approval pending). In each instance, the investigator will describe the complete protocol to the prospective participant. The subjects will then be given a written informed consent form that has been approved by the Vanderbilt Institutional Review Board. The subject will be given adequate time to read the consent form, ask questions, and if satisfied by the responses, sign the form. Consent or refusal to participate in this study will not affect medical care. No modifications or waiver of the elements of consent have been authorized, nor will any be necessary in the execution of this study.

POTENTIAL RISKS:

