Blood drawing and insertion of venous catheters are uncomfortable and may cause bruising, bleeding, permanent damage to the vessel and in rare instance, infection. The risk of bleeding can be prevented by tight compression of the site. Experienced personnel will place all intravascular lines using sterile technique.

Consuming a sodium- and caffeine-controlled diet might not be to the subject's taste preferences. If a subject drinks caffeinated beverages regularly and stops caffeine intake suddenly, he/she might have headaches and fatigue for a few days. These symptoms can be avoided by cutting down gradually on the amount of caffeine in the diet.

Stopping medications might cause a temporary worsening of symptoms for patients. Careful monitoring of blood pressure and heart rate will permit immediate attention and termination of the protocol when necessary.

Collection of urine can be inconvenient.

The seated oral medical trials are tedious and boring because they require being seated for an extended period of time while blood pressure is monitored.

When any medication is used in testing, there is a small risk of an unforeseeable life-threatening allergic reaction. Side effects associated with specific medications are listed below. Side effects are listed as common, uncommon, and rare.

Domperidone – common: dry mouth, abdominal cramps, diarrhea. Uncommon: loss of balance or muscle control, swelling of mouth, increased breast milk flow, headache, hives, hot flashes. Rare: pounding or racing heart beat, swelling of extremities, change in appetite, constipation, dizziness.

α -Methyldopa – common: weakness, distention of lower abdomen, constipation, swelling of the lower extremities, fever and depression, anxiety, nightmares, being sleepy or drowsy, headache and dry mouth. Uncommon: dizziness, gas, diarrhea, chest pain, stuffiness of the nose, low blood pressure on standing, low heart rate, nausea or vomiting, abnormal liver function tests. Serious or life-threatening: extremely rare reactions are fatal liver damage and fatal inflammation to the heart.

Carbidopa – only reported to have adverse effects when it is given with the drug levodopa for Parkinson's disease. Common adverse events with the carbidopa-levodopa combination include dyskinesias and nausea. Less common adverse effects are psychotic episodes, depression and dementia.

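### The chronic trial schedules no liver test over 56 dosing days, although three of the seven active drugs have a listed liver-test effect; adding one at the existing blood-collection days is a modest, cheap safety gain

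*Combined protocol and SAP*

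**What the plan says.** **Drugs and their liver effects.** The section on single-dose drug trials names seven active drugs and placebo. Potential Risks lists a liver-test effect for three of them:

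- Alpha-methyldopa: the entry ends its uncommon effects and opens its serious ones with "abnormal liver function tests. Serious or life-threatening: extremely rare reactions are fatal liver damage".
- Atomoxetine: abnormal liver tests, listed as rare.
- L-DOPS: raised liver enzymes, among side effects described as rare. The drug is investigational and has no FDA approval.

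**Chronic trial.** The Chronic trial table has drug taken on Days 0 to 55 and blood collected on Days 0, 14, 28 and 56. At these visits patients are assessed as follows: "they will be evaluated by a posture study, 24-hour urine collection and assessment of their symptoms". On dosing: "The dose of the medication will be adjusted after two and four weeks of treatment if there has been insufficient improvement in blood pressure", or in symptoms.

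**Laboratory lists.** Research Materials states: "The blood will be analyzed for catecholamines, renin and aldosterone". Core Lab Utilization and Other Support request catecholamines, urinary electrolytes and creatinine, aldosterone, renin and pregnancy tests. No liver test appears in any of these places.

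**Safeguards.** Subjects must be "free of pulmonary, renal, hematopoietic, hepatic and cardiac disease" at entry. What follows a single-dose trial is decided "Depending on how well the drug is tolerated and the degree of improvement in orthostatic vital signs and symptoms following the drug". The efficacy condition is in Experimental Design and Methods: "A drug or drugs effective at preventing an orthostatic fall in blood pressure might then be tested in a 5-day crossover trial". L-DOPS is started low and titrated so as to avoid adverse effects. The Protection paragraph relies on vital signs, and the Data Safety Monitoring Plan provides a bi-monthly review of data and immediate review of serious events.

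**The concern.** The protocol identifies a laboratory effect for drugs that it may give for eight weeks, but it plans no measurement that could show that effect. Blood pressure, heart rate and symptom questions do not reveal an enzyme rise in a patient who feels well.

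The adjustment rule adds to this. The dose is changed when the response is insufficient, which by inference usually means an increase. As written, that increase can be made with no liver result, and dosing then continues for up to four more weeks.

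L-DOPS makes the point practical. Preliminary Studies says of it: "It might also improve the blood pressure in patients that have profound orthostatic hypotension but do not appear to have complete DBH deficiency". These are close to the patients enrolled here, so L-DOPS is a plausible chronic drug, and atomoxetine remains available too. What is at stake is patient safety in the chronic phase; the trial's efficacy comparison is not affected.

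**Working it through.** The plan states no figure for this point, so there is none to reproduce. The check is a count from the documents, followed by an illustration on assumed rates.

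**1. Drugs.** Seven active drugs: domperidone, metyrosine, L-DOPS, alpha-methyldopa, L-dopa, carbidopa and atomoxetine. Those with a listed liver-test effect: L-DOPS, atomoxetine and alpha-methyldopa, so 3 of 7.

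**2. Exposure (Chronic trial table).** Days 0 to 55 = 56 dosing days. From the second adjustment, Days 28 to 55 = 28 dosing days.

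**3. Tests.** Four blood-collection days (0, 14, 28, 56), none with a liver test. Two possible adjustments (Days 14 and 28), neither preceded by a liver result. A patient may have none, one or both adjustments.

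**4. Would a planned liver test be written down?** The laboratory lists alone are weak evidence: they omit hematocrit although a value below 35 is an exclusion. The urine pregnancy test is a better comparison, because it is a safety test repeated during the study. It appears in the methods text, at all four admissions in the Chronic trial table, and in Other Support (84 tests). A repeated liver test would be expected to appear in the same way.

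**5. Does another safeguard cover it?** The hepatic criterion applies at entry, with no test or limit given. The tolerability and efficacy conditions follow a single dose or five days of drug. The data review sees only what was collected. None is a liver check during chronic dosing.

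**6. Runs of dosing without a liver result** (counting the dose on a test day as taken after the draw):

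| Period | Dosing days | Result at end, now | Result at end, with tests on Days 0, 14, 28, 56 |
|---|---|---|---|
| Days 0-13 | 14 | none | yes |
| Days 14-27 | 14 | none | yes |
| Days 28-55 | 28 | none | yes, but after the last dose |

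The longest run is 14 + 14 + 28 = 56 days now and 28 days with the tests. Dosing before the first adjustment is 14 days either way. The run before the second falls from 28 to 14.

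**7. Illustrative size.** Assumptions: rare = 0.1-1%, uncommon = 1-5%, and n chronic patients all on a drug of that class. Expected cases = n × p; chance of at least one = 1 − (1 − p)^n.

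| n | Rare: expected | Rare: at least one | Uncommon: expected | Uncommon: at least one |
|---|---|---|---|---|
| 5 | 0.005-0.05 | 0.5-4.9% | 0.05-0.25 | 4.9-22.6% |
| 10 | 0.01-0.10 | 1.0-9.6% | 0.10-0.50 | 9.6-40.1% |
| 25 | 0.025-0.25 | 2.5-22.2% | 0.25-1.25 | 22.2-72.3% |

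For example, n = 25 and p = 0.01 give 25 × 0.01 = 0.25 and 1 − 0.99^25 = 22.2%. The 25-patient row is an upper bound, since it puts every planned subject into a phase that the protocol makes conditional. The uncommon columns apply only to alpha-methyldopa.

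**The case against.** **The case rests mainly on two drugs with a rare effect.** Alpha-methyldopa is the only one with a more frequent liver effect or with liver damage listed, and it is an unlikely chronic drug: Potential Risks lists low standing blood pressure for it, while progression requires that the drug prevent an orthostatic fall. This stands. A reader might infer from the count of three drugs and the mention of fatal liver damage that serious liver injury is a realistic prospect here. The documents do not support that: for L-DOPS and atomoxetine they list only rare test abnormalities.

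**Testing may happen outside the plan.** Hematocrit and freedom from hepatic disease must be assessed somehow, and neither method is shown. The companion protocol on the pathophysiology of orthostatic hypotension is not available and might supply a baseline. This also stands, so one cannot conclude that no patient would have a liver test. What can be said is that none is scheduled in the visible plan. A test in the companion study would precede chronic dosing and would not cover it.

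**The remedy does less than it may seem to.** Dosing ends on Day 55, so the Day 56 result cannot change exposure, and the 28 days after the second adjustment keep no on-treatment result. Only the Day 14 and Day 28 panels can alter dosing once it has started. A reader might take the fix as shortening untested dosing from 56 to 14 days; step 6 of the working shows that it does not.

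**Holding a dose has a cost.** The affected patient has severe orthostatic hypotension and has already responded poorly. If a result is late, the increase might fall after the admission. This is fair, and it is why same-day reporting matters.

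These points limit the benefit. None supplies a liver result before a dose increase.

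**Conclusion.** The point holds as a modest safety improvement that should be made. The protocol names a liver-test effect for 3 of 7 active drugs, schedules no liver test in 56 days of chronic dosing, and allows two dose adjustments on blood pressure and symptoms alone.

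It is not a demonstrated harm. The documents do not say how often enzyme rises occur, when they appear, whether they depend on dose, or how many patients reach the chronic trial. On the assumed rates, fewer than one case is expected in every row of the illustration except the top of the range with all 25 patients on alpha-methyldopa (1.25), the least plausible mix. Reading the dose adjustment as an increase is an inference from its trigger.

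The gain from the fix is a baseline, a liver result at each adjustment point, and a longest untested run of 28 days in place of 56.

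**What to change.** For chronic-trial patients on L-DOPS, atomoxetine or alpha-methyldopa, add one tube for liver enzymes to the blood already collected:

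- **Day 0**, before the first chronic dose: baseline.
- **Days 14 and 28**: result reviewed before any dose increase; if it is late, hold the increase until it arrives.
- **Day 56**: end-of-treatment check, with follow-up if abnormal.

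State in the amendment the investigator-set value that blocks an increase or stops the drug. Add the test to the Chronic trial table and Research Materials, and bring the results into the review under the Data Safety Monitoring Plan.

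**Cost.** Four panels per patient with one chronic trial: 5 × 4 = 20, 10 × 4 = 40 or 25 × 4 = 100 panels, against 700 aldosterone assays already requested. It needs a short amendment, a few millilitres more blood per draw and same-day results on two visits. No additional visit or venepuncture is planned. A dose increase may be delayed briefly, and a late result could push it beyond the admission. Drawing at the Day 13 and Day 27 admissions would ease the timing but would add a venepuncture.
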